## Protocol Synopsis

Title	A Biomarker-Based Pilot Study of Mouse Subcutaneous Immunotherapy in Mouse Sensitive Adults with Asthma
Short Title	Subcutaneous Immunotherapy for Mouse in Adults (SCITMO)
Clinical Phase	I/IIa
Number of Sites	Multiple
Study Objectives	
The primary objective of the study is to assess if treatment with mouse SCIT, using the per protocol allergenic extract doses, is safe. This will be done by determining the rate of related adverse events and serious adverse events in the course of treatment.
 
Secondary objectives are:
 
 
1. To determine whether a 24 week treatment with mouse SCIT, using the per protocol allergenic extract doses, will induce a 3-fold increase in mouse-specific serum IgE.
 
2. To determine whether a 24 week treatment with mouse SCIT, using the per protocol allergenic extract doses, will induce changes in the serum levels of mouse-specific IgG and IgG4.
 
3. To determine whether a 24 week treatment with mouse SCIT, using the per protocol allergenic extract doses, will inhibit the in the in-vitro mouse antigen binding to B-cells.
 

Study Design	This is an open label trial of mouse allergenic extract administered by subcutaneous injection in 10 adults ages 18 to 55 years with asthma and mouse sensitivity. It is designed to study the safety of this therapy as well as biomarkers of the immune response.
Primary Endpoint(s)	The number of reported adverse events and serious adverse events, including their severity, seriousness, and treatment relatedness.
Secondary Endpoint(s)	
 
1. Changes in levels of mouse specific IgE observed after initiation of study treatment.
 
2. Changes in mouse specific IgG and IgG4.
 
3. Change in in-vitro mouse antigen binding to B-cells
 

Accrual Objective	Approximately 10 - 12
Study Duration	12 months

Treatment Description	Nonstandardized glycerinated mouse epithelial allergenic extract by subcutaneous administration in escalating doses up to 0.4 ml of 1:20 wt/vol.
Inclusion Criteria	
 
1. Male or female adults, 18 through 55 years of age at recruitment.
 
2. Have a history of asthma for a minimum of 1 year before study entry.             
 
a. A diagnosis of asthma will be defined as a report by the participant that they have had a clinical diagnosis of asthma made by a clinician over a year ago.
 
b. The participant must have persistent asthma defined by the current need for at least 100 mcg fluticasone per day or the equivalent of another inhaled corticosteroid.
 
c. The participant's asthma must be well controlled as defined by:                     
 
i. A FEV1 greater than or equal to 70% predicted with or without controller medication (see Section 8.2).
 
ii. An Asthma Control Test (ACT) score <math>\geq 20</math>.
 
 
 
 
 
3. Are sensitive to mouse as documented by a positive (<math>\geq 3</math> mm greater than negative control) skin prick test result (using the same extract used for immunotherapy) and detectable mouse specific IgE (<math>\geq 0.10</math> kUA/L).
 
4. Have no known contraindications to therapy with glycerinated mouse allergenic extract or placebo.
 
5. Are willing to sign the written Informed Consent prior to initiation of any study procedure.
 

Exclusion Criteria	
 
1. Are pregnant or lactating. Females must be abstinent or use a medically acceptable birth control method throughout the study (e.g. oral, subcutaneous, mechanical, or surgical contraception).
 
2. Cannot perform spirometry at Screening.
 
3. Have an asthma severity classification at Screening of severe persistent, using the NAEPP classification, as evidenced by at least one of the following:             
 
a. Require a dose of greater than 500 mcg of fluticasone per day or the equivalent of another inhaled corticosteroid.
 
b. Have received more than 2 courses of oral or parenteral corticosteroids within the last 12
 
 
 

	
months.
 

c. Have been treated with depot steroids within the last 3 months.

d. Have been hospitalized for asthma within the 6 months prior to Screening.

e. Have had a life-threatening asthma exacerbation that required intubation, mechanical ventilation, or that resulted in a hypoxic seizure within 2 years prior to Screening.

 

4. Do not have access to a phone (needed for scheduling appointments).

5. Have received allergen immunotherapy (SLIT or SCIT) in the last 12 months prior to Screening or who plan to initiate or resume allergen immunotherapy during the study.

6. Have previously been treated with anti-IgE therapy within 1 year of Screening.

7. Have received an investigational drug in the 30 days prior to Screening or who plan to use an investigational drug during the study.

8. Refuse to sign the Epinephrine Auto-injector Training Form.

 
Participants who meet any of the following criteria are not eligible for enrollment and may not be reassessed. Participants are ineligible if they:
 

9. Do not primarily speak English.

10. Plan to move from the area during the study period.

11. Have a history within the past 5 years of idiopathic anaphylaxis or anaphylaxis grade 2 or higher as defined in section 9.2.4.2, Grading Criteria for Anaphylaxis.

12. Have unstable angina, significant arrhythmia, uncontrolled hypertension, history of autoimmune disease, or other chronic or immunological diseases that in the opinion of the investigator might interfere with the evaluation of the investigational agent or pose additional risk to the participant.

13. Are using tricyclic antidepressants or beta-adrenergic blocker drugs (both oral and topical).

14. Have not received and refuse to receive the Flu Vaccine

--	--

Study Stopping Rules	
Study enrollment and treatment will be suspended pending expedited review of all pertinent data after the occurrence of:
 

1) 1 death regardless of relationship to the investigational agent

2) 1 anaphylactic reaction grade 3 possibly related to the investigational agent

3) Either of the following events, if considered related to the study procedures or treatments, in at least 2 participants:

a) Anaphylactic reaction grade 2.

b) Hypotensive shock: Drop in blood pressure: Systolic < 90 mm Hg or < 80% of baseline, whichever is higher, and diastolic blood pressure < 60 mm Hg-absolute.

----------------------	--

## Glossary of Abbreviations

AE	Adverse Event/Adverse Experience
CFR	Code of Federal Regulations
CRF	Case Report Form
CTCAE	Common Terminology Criteria for Adverse Events
DAIT	Division of Allergy, Immunology, and Transplantation
DSMB	Data Safety Monitoring Board
FDA	Food and Drug Administration
GCP	Good Clinical Practice
HIPAA	Health Insurance Portability and Accountability Act
ICH	International Conference on Harmonization
IND	Investigational New Drug
IRB	Institutional Review Board
MOP	Manual of Procedures
MSD	Maximum Study Dose
NAEPP	The National Asthma Education and Prevention Program
NIAID	National Institute of Allergy and Infectious Diseases
NIH	National Institutes of Health
OHRP	Office for Human Research Protections
PHI	Protected Health Information
PI	Principal Investigator
SACCC	Statistical and Clinical Coordinating Center
SAE	Serious Adverse Event
SAR	Suspected Adverse Reaction
SCIT	Subcutaneous Immunotherapy
SLIT	Sublingual Immunotherapy
SUSAR	Suspected Unexpected Serious Adverse Reaction

## 1 Background and Rationale

### 1.1 Background and Scientific Rationale

Mouse allergen has received much less attention than cockroach allergen, despite the fact that findings to date suggest that exposure to this pest allergen also plays an important role in asthma morbidity. Like Bla g 1, the major mouse allergen, Mus m 1, is detectable in a very high proportion of inner-city homes and is present in 100-fold higher concentrations in inner-city homes compared to suburban homes. Mouse allergen exposure is also a well-recognized risk factor for occupational asthma, with 30-50% of laboratory mouse workers experiencing mouse-related allergic symptoms, and 20% with skin test sensitivity to mouse. More compelling with regard to inner-city asthma is the fact that Mus m 1 levels in many inner-city homes are comparable to levels found in occupational settings, where mouse allergen is known to cause both acute and chronic asthma. In addition, the prevalence rate of mouse skin test sensitivity in patients with asthma living in the inner-city is similar to that found in occupational settings. In fact, cross-sectional studies of inner-city asthmatics have found mouse skin test sensitization rates of 17-50%. The fact that both the prevalence of mouse sensitization and the intensity of Mus m 1 exposure in the inner-city are similar to that observed in occupational settings – where mouse allergen is a known cause of asthma symptoms – provides a compelling rationale for a causal link between mouse allergen exposure and asthma in the inner-city.

As with cockroach allergen, the only currently available treatment for mouse allergy is avoidance and eradication. Studies aimed at the eradication of mice in home environments have had some success; however, the fact remains that multifaceted environmental eradication programs are extremely difficult to implement in inner city environments with limited resources. As such, a more definitive treatment may be desensitization of patients with mouse allergy using allergen immunotherapy.

Given these data, a major ICAC goal is to conduct a large multi-center efficacy trial of immunotherapy, including mouse allergen, in inner-city asthma. While we have pursued the possibility of using sublingual immunotherapy (SLIT) given its excellent safety profile, data from the BioCSI and BioCSI2 studies (ICAC-12 and ICAC-17) of cockroach SLIT have raised the possibility that SLIT for cockroach may not be effective due to limitations in the maximum doses that can be provided with currently available extracts. These studies have also generated concerns about the likelihood of compliance with daily SLIT therapy, an issue that may both reduce efficacy and potentially increase risk. Given those concerns, a pilot study of cockroach SCIT was also conducted in 10 adults (SCITCO, ICAC-18) with a primary focus on safety in an effort to lay the groundwork for an efficacy study using SCIT. The SCITCO study demonstrated an excellent safety profile, as well as robust biomarkers of immunologic response. Given that mouse allergen is also a key inner-city allergen, and that there is a paucity of experience with mouse immunotherapy, the current study is designed to provide similar safety and immunologic data for mouse that SCITCO provided for cockroach.

While studies of cockroach and mouse are limited, there is a vast clinical and research experience with the use of SCIT for the treatment of asthma and allergic rhinitis, as well as stinging insect hypersensitivity. While there is a higher risk of systemic reactions with SCIT compared to SLIT, the overall safety profile of SCIT is very favorable, as is the overall SCIT risk benefit ratio given the marked improvements in disease activity demonstrated in most studies. As with SLIT, the efficacy of SCIT depends on the use of adequate dosages, but we are confident that for SCIT the available extracts will prove adequate in this regard.

The rationale for this study is therefore that immunotherapy, focused on key indoor allergens, will be effective for the treatment of inner-city asthma, and that SCIT is the best option. This preliminary study is a logical next step, necessary to provide data regarding both safety and immunogenicity before proceeding to an efficacy trial.

### **1.2 Rationale for Selection of Investigational Product or Intervention**

The study agent for this protocol is 1:20 w/v glycerinated mouse epithelial allergenic extract administered by the subcutaneous route purchased from Greer Laboratories (Lenoir, NC). Mouse Epithelia (*Mus musculus*) allergic extract is approved in the United States for diagnostic skin testing and immunotherapy by subcutaneous injection (US License NO. 308). While mouse SCIT has undergone little prior study and specific dosing guidelines have not been established, there is a large body of literature for other allergens that can be applied to choose a dose schedule for this protocol that should maximize safety and efficacy. For other allergens, maintenance doses of major allergens ranging from 5 to 15 micrograms have proven effective and our dosing strategy will seek to achieve a maintenance dose within this range, with a secondary goal of minimizing injection volume so that this same dose could eventually be applied to a multi-allergen protocol in pediatric patients.

### **1.3 Preclinical Experience**

Not applicable.

### **1.4 Clinical Studies**

Only one study of mouse immunotherapy has previously been published. That study was conducted in 23 laboratory animal workers, 11 of whom received immunotherapy with 12 different extracts (five mouse, six rat, one rabbit), and 12 were matched untreated controls. The maximum weekly immunotherapy dose for the different allergens ranged from 2,000 to 10,000 protein nitrogen units (PNU). Among the treated patients, nine of 11 subjectively improved with immunotherapy and blocking antibody titers were significantly elevated in the treated subjects compared to the controls (specific data on mouse were not provided). There were no systemic reactions reported, nor any need to discontinue dosing due to adverse reactions.

It is important to recognize, however, that even though there are a minimal data regarding mouse, there is a vast body of literature and clinical experience with the use of SCIT for other allergens. A recent practice parameter detailed the use of SCIT for inhalant allergens as well as stinging insects. In addition, meta-analyses have confirmed the effectiveness of SCIT for the treatment of asthma, allergic rhinitis, and stinging insect hypersensitivity. A 2003 Cochrane review of 75 trials, including 3188 patients with asthma, found that overall SCIT led to a significant reduction in asthma symptoms, medication use, and bronchial hyperreactivity. For example, in that review, it was determined that it would have been necessary to treat 4 patients with immunotherapy to avoid 1 deterioration in asthma symptoms and 5 patients to avoid 1 requiring increased asthma medication.

## **2 Study Hypotheses/Objectives**

### **2.1 Hypotheses**

The two hypotheses tested by this study are 1) Subcutaneous treatment with mouse extract can be safely administered in adults with mouse sensitivity and 2) Subcutaneous treatment with mouse extract can induce significant changes in serum biomarkers indicative of immunologic activity.

### **2.2 Primary Objectives**

The primary objective of this pilot study is to assess if treatment with mouse SCIT, using the per protocol allergenic extract doses, is safe. This will be done by determining the rate of related adverse events and serious adverse events in the course of treatment.

[figure not shown]
### 2.3 Secondary Objective(s)

1. To determine whether a 24 week treatment with mouse SCIT, using the per protocol allergenic extract doses, will induce a 3-fold increase in mouse-specific serum IgE.
2. To determine whether a 24 week treatment with mouse SCIT, using the per protocol allergenic extract doses, will induce changes in the serum levels of mouse-specific IgG and IgG4.
3. To determine whether a 24 week treatment with mouse SCIT, using the per protocol allergenic extract doses, will inhibit the in-vitro mouse antigen binding to B-cells.

## 3 Study Design

### 3.1 Description of Study Design

This study is an open label multi-site trial of mouse allergenic extract administered by subcutaneous injection in approximately 10 - 12 adults ages 18 to 55 years with asthma. The study will be based on a continuous treatment schedule with mouse allergenic extract for a period of approximately 24 weeks. It is primarily designed to study the safety of this therapy.

There will be a Screening Visit followed by a Dose Initiation Visit, at which the subject will receive their first injection. Up to 2 doses of SCIT will be given weekly during dose escalation, separated by a minimum of 2 days. Dose escalation will occur over a minimum of 11 weeks. Dose escalation can be delayed at any point if there are excessive large local reactions or other concerns, although to continue on to maintenance each subject will need to reach the maintenance dose in a maximum of 18 weeks. Once the maintenance dose is achieved, bi-weekly visits will continue to complete a total of 24 weeks of treatment.

Blood will be collected at baseline and then monthly for assessment of biomarkers of allergen immunotherapy, including mouse specific IgE, IgG, IgG4, and inhibition of mouse antigen binding to B-cells. Mouse skin testing will be performed at screening. (See Visit Activities Summary, Appendix A)

Adverse events (AEs) will be assessed at each study visit. Allergy and asthma symptom questionnaires will also be administered throughout the study.

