### **8.6 Final Study Visit**

A final study visit will be performed for all participants who began study treatment, regardless of whether or not they entered or completed the 24 week treatment course. The final visit will include:

- Final physical exam
- Blood draw
- Spirometry
- Pregnancy test (females only)

Participants recording only mild or no symptoms at the last office visit will be discharged from the study. Participants recording moderate or severe symptoms at the last office visit will require follow-up as described in 12, Safety Monitoring and Reporting.

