### **8.10 Visit Windows**

During dose escalation, 2 injections will be given each week separated by at least 2 days. Dose escalation may be accomplished over a maximum of 18 weeks.

Bi-weekly maintenance visits will be scheduled within the second calendar week following the previous maintenance visit. See the MOP for details regarding visit scheduling.

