## **9 Mechanistic Assays**

Whole blood will be collected by venipuncture every month during the maintenance period, and will be processed according to the MOP. The blood will be tested for biomarkers of allergen immunotherapy, such as mouse-specific IgE, IgG, IgG4 antibodies, and in-vitro mouse antigen binding to B-cells (see Appendix A).

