### Appendix A: Schedule of Procedures/Evaluations

Visit Number	Screening	Dose Initiation	Bi-Weekly Dose Escalation Visits	Bi-Monthly Maintenance Visits	Final Visit
Informed consent, screening	X				
Medical history	X				
Physical exam 	X	X	X	X	X
Vital signs 	X	X	X	X	X
Flu vaccine 	X				
Spirometry	X				X
Peak flow	X	X	X	X	X
Adverse event assessment		X	X	X	X
Symptom questionnaires	X	X	X	X	X
Allergen skin test	X				
Blood collection 	X	X		X	X
Pregnancy test 	X	X	X	X	X
Dose escalation 		X	X		
Injection		X	X	X	

 A detailed physical exam will occur at Screening and at the Final Visit. A more limited physical exam will be completed at every injection visit.

 Height and weight will be assessed at Screening only.

 Blood will be drawn at screening, at baseline and monthly after the maintenance dose has been reached for assessment of biomarkers of allergen immunotherapy such as IgE, IgG, and IgG4.

 Pregnancy testing will be done monthly after dose initiation in females.

 Dose Escalation will normally take 11 weeks, but can take place over up to 18 weeks, if needed.

 Flu vaccine will be given to participants when it becomes available if they have not already received the vaccine.

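### Do the conflicting biomarker blood schedules, and the lack of a named analysis week in Section 13.4.3, undermine the 24-week IgE objective?

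*Combined protocol and SAP*

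**What the plan says.** Three places set the timing of biomarker blood.

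- Section 3.1: "Blood will be collected at baseline and then monthly for assessment of biomarkers of allergen immunotherapy". The same paragraph then refers to Appendix A.
- Section 9: "Whole blood will be collected by venipuncture every month during the maintenance period".
- Appendix A, footnote 3: "Blood will be drawn at screening, at baseline and monthly after the maintenance dose has been reached for assessment of biomarkers of allergen immunotherapy". The blood-collection row has no mark in the dose-escalation column.

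Appendix A also gives the length of escalation ("Dose Escalation will normally take 11 weeks, but can take place over up to 18 weeks, if needed"). Section 8.10 leaves the detail to a manual that is not among the documents: "See the MOP for details regarding visit scheduling".

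On the analysis side, the first secondary objective in Section 2.3 asks whether 24 weeks of treatment "will induce a 3-fold increase in mouse-specific serum IgE", and Section 13.1 repeats that this is measured over 24 weeks. Section 13.4.3 promises three things: summary statistics for the secondary endpoints, exact 95% confidence intervals for any endpoint that is a proportion, and absolute and relative changes from baseline for IgE, IgG and IgG4. It names no visit. Section 13.4.1 analyses everyone who received the first injection.

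On final samples, Section 8.6 states: "A final study visit will be performed for all participants who began study treatment, regardless of whether or not they entered or completed" the 24-week course. Section 6.5 asks for a final blood sample at discontinuation, and Section 8.7 describes a separately named Early Termination Visit.

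**The concern.** Read alone, Section 3.1 implies biomarker samples during escalation, and Section 9 and Appendix A imply none. The blank in Appendix A looks deliberate, because another monthly item is marked in the same escalation column ("Pregnancy testing will be done monthly after dose initiation in females"). A site could therefore follow either text, and the number and timing of samples would differ. Under Appendix A they would also depend on how quickly a participant escalates.

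The second worry is which sample answers the 24-week question. Everyone dosed is in the analysis population, most early stoppers would give a last blood sample, and Section 13.4.3 does not say that the last sample must come from week 24. A sample taken after a few weeks of very dilute extract could then be summarised beside true week-24 values and pull the estimated IgE rise down. With about 10 participants, one or two such values would show.

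**Working it through.** **1. Injection count.** Table 8.5.1 lists 22 escalation doses. Maintenance every 2 weeks from week 13 gives weeks 13, 15, 17, 19, 21 and 23, which is 6 doses. 22 + 6 = 28, matching the approximate figure in Section 13.6.

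**2. Draws under each text.** Assume a month of 4 weeks and a final visit at week 24.

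- Section 3.1: weeks 4, 8, 12, 16, 20, 24 = 6 draws after baseline. Two fall within an 11-week escalation and four within an 18-week one.
- Section 9 and Appendix A, maintenance dose reached at week 11: weeks 11, 15, 19, 23, 24 = 5 if a draw is taken on reaching it. Starting a month later gives weeks 15, 19, 23, 24 = 4, or 3 if weeks 23 and 24 are combined.
- Section 9 and Appendix A, reached at week 18: weeks 18, 22, 24 = 3, or weeks 22, 24 = 2.
- Difference: 6 − 5 = 1 to 6 − 3 = 3 draws per participant (11 weeks); 6 − 3 = 3 to 6 − 2 = 4 (18 weeks).

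With a calendar month (52/12 = 4.33 weeks) and the final visit counted, the totals are 6 against 3 to 4 and 2 to 3, so the picture is the same. Baseline and week 24 are present under every version.

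**3. What the escalation draws would measure.** Express Table 8.5.1 as volume of the 1:1 concentration.

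- Doses 1–16: 0.75 × (0.0001 + 0.001 + 0.01 + 0.1) = 0.0833 ml.
- Doses 17–22: 0.05 + 0.10 + 0.15 + 0.20 + 0.30 + 0.40 = 1.20 ml.
- Maintenance: 6 × 0.40 = 2.40 ml. Total: 3.683 ml.
- Share given by week 4: 0.000825 / 3.683 = 0.02%. By week 8: 0.0833 / 3.683 = 2.3%. By week 11: 1.283 / 3.683 = 35%.

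On the normal schedule the draws at weeks 4 and 8 come before nearly all of the exposure. Cumulative volume is only a rough guide to biomarker response, and the documents give no better one.

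**4. What pooling early samples would do.** The documents give no expected ratios, so these are assumptions: completers have an IgE geometric mean ratio of 3.0, and k early stoppers have ratio f. The pooled ratio is 3^((n−k)/n) × f^(k/n).

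- Stoppers replaced, so 10 completers plus k, with f = 1: 3^(10/11) = 2.71, 3^(10/12) = 2.50, 3^(10/13) = 2.33 for k = 1, 2, 3.
- Stoppers not replaced, n = 10 in all, f = 1: 3^0.9 = 2.69, 3^0.8 = 2.41, 3^0.7 = 2.16.
- Not replaced, f = 1.5: 2.80, 2.61, 2.44.
- Proportion with a 3-fold rise: if 6 of 10 completers reach it, 60% (exact 95% CI 26% to 88%); adding 2 stoppers who do not, 6 of 12 = 50% (21% to 79%).

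Both replacement cases are shown because Section 6.5 rules out replacement after the first 8 injections, while Section 11.3 replaces those who withdraw until the sample size is reached.

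**5. Does the plan call for pooling?** No section does. The horizon is stated in Sections 2.3 and 13.1, and relative change and exact intervals for proportions are already in Section 13.4.3. The early-termination visit has its own name in Section 8.7, although that section gives no analysis rule. The number of early samples is also limited: Section 8.7 allows a telephone assessment for those who will not attend, and Section 8.8 stops all procedures after pregnancy.

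**The case for a change.** The case for a change is that biomarker response is one of the two hypotheses in Section 2.1, and Section 1.1 says immunogenicity data are needed before an efficacy trial. Section 11.2 lists twelve grounds for withdrawal, so early stoppers are foreseeable, and with about 10 people each sample counts. Nothing in Section 13.4.3 forbids using an early final sample as the follow-up value. It does not name the 3-fold proportion, and its sentence on change from baseline omits B-cell binding. Correcting the text would cost only words.

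Much of the factual part stands. The sentence in Section 3.1 is inconsistent with Section 9 and Appendix A, and Section 13.4.3 names no analysis visit. The step from there to a needed change does not stand. Aligning Section 3.1 with Appendix A would alter no result. Adding draws during escalation would cost 10 to 36 extra samples across 10 to 12 people (1 to 3 each), or 30 to 48 (3 to 4 each), plus assays, to describe a time course that no objective asks for. A fixed rule restricting the summary to completers would be a choice in its own right, because it selects those who tolerated treatment. B-cell binding is covered by the general promise of summary statistics for secondary endpoints.

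**Conclusion.** No change to the plan follows. The schedule conflict is a clerical slip in a design summary: the section it sits in refers to Appendix A, and Appendix A and Section 9 agree with each other. The missing analysis visit is a gap that analysts would fill sensibly. Week 24 is the stated horizon, Appendix A lists a baseline draw separate from screening, which is the Dose Initiation draw of Section 8.4, and early samples can be listed by the week they were taken.

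The size is modest: 1 to 4 draws per participant between the two schedules. If early samples were pooled, a shift from 3.0 to between about 2.2 and 2.8 would occur under the assumed ratios with one to three stoppers. That range depends on invented inputs and on a pooling step the plan does not prescribe. The endpoints are secondary and descriptive, completers' change to week 24 is estimable under either schedule, and the primary safety endpoint and Table 13.6 are untouched. The conclusion assumes that sites work from Appendix A and that the final-visit sample of completers falls at about week 24. The manual that holds the visit-scheduling detail was not available to confirm either point.
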